Last 10 Subjects. These subjects will take part in a double-blind, controlled, randomized, cross-over study over 3 sessions following their screening visit. At session 1 subjects will undergo electrical dose titration with the tDCS electrode configuration resulting from the 3 rounds of optimization using the same procedure as in the first 30 subjects to determine the lowest well-tolerated dose that suppresses the pupil dilation response to the Anxiety Task or Auditory Oddball Test, except that a maximum of 5 tDCS dosages will be tested at this session. At the second and third sessions (1 week apart) subjects will receive doseoptimized tDCS and the control treatment with order randomized along with 7.5% CO₂ (to evoke an LC response) for 20 minutes. The 7.5% CO₂ will be delivered pre-mixed as provided by Airgas. 7.5% CO₂ is commonly and safely used in the field of study. A mixture of CO₂ 7.5%/O₂ 21%/N 71.5% will be purchased premixed from Airgas and shipped to UCSF. At these sessions, the VAS-A and STA-I will be administered 5 minutes prior to and just after the 20 minute session and VAS-A will also be obtained at 5, 10, 15, and 20 minute points of the CO₂ inhalation. tDCS will be administered during the last 5 minutes of the 20 minute CO₂ inhalation period. Subjects will be monitored for an hour post-session for safety and will undergo study physician assessment to determine suitability to leave. Following the 2nd treatment session participation will end except that subjects will be called the next day to assess for adverse effects and appropriate care will be given if any are found.

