R33 Phase: 60 subjects will participate in a double-blind, randomized, controlled, parallel-group trial. They will be randomized to either active or control treatment and at the first post-screening visit they will undergo electrical dose titration as described above for the treatment they are randomized to. For all titrations, during the 5 minutes between tDCS treatments an unblinded member of the study team not having contact with the subjects will compute their Anxiety Task or Auditory Oddball Test response (these tests will be used to determine optimal dosing in terms of the tDCS level that blocks the pupil response in these tests) and convey to the tDCS treatment physician whether to continue or stop titration. Subjects randomized to the control treatment will undergo a sham titration where the stop level will be randomly selected from the distribution of titration outcomes occurring in the R21 phase. Subjects will then return in 1 week and undergo optimal dose tDCS or control treatment for a single treatment session as described in the prior paragraph. Primary outcome will be the VAS-A "fearful" rating obtained at the end of tDCS/CO₂ inhalation. Anxiety Task or AOT pupil responses will be obtained every 10 minutes after the end of the tDCS/CO₂ inhalation period to map the duration of persistent effects on LC (heart rate and skin conductivity will also be obtained as exploratory measures). At the end of this session participation will end except that subjects will be called the next day to assess for adverse effects and care given if necessary. Data from the R21 phase will be used to provide justification for the larger R33 study, and prior to initiation of the R33 phase, the study will be submitted to the IRB for review/approval.

8.5 BACKGROUND AND SIGNIFICANCE: Briefly provide the background and significance of this study (e.g.

why is this study needed) (space limit: one half page):

If this is a first in humans study, please summarize the safety data from the animal studies. For pediatric drug or device studies, please identify if this is the first study in pediatric populations.

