3. **Visual Analogue Scale for Anxiety (VAS-A).** The VAS-A is the primary measure of clinical symptoms of Acute Fear in both the R21 and R33. It has been used extensively as an indicator of acute fear symptoms. It is included because it provides a reliable indicator of rapid changes of affective state and is sensitive to the fear-inducing effects of 7.5% CO₂ in healthy volunteers. VASA consists of 11 items for 11 different symptoms (anxious, alert, fearful, relaxed, happy, feel like leaving, paralyzed, tense, nervous, irritable and worried) where for each item a mark is made on a 100 mm line scaled from 0 (not at all) to 100 (the most ever) to indicate symptom severity. The "Fearful" item will be used as the single primary endpoint due to its being consistently significantly increased in prior studies of CO₂ administration to healthy controls and evidence that anxiolytics can prevent 7.5% CO₂ mediated increases in this measure. The other 10 VAS-A items will be secondary outcomes. For each CO₂ administration ratings will be carried out at baseline (5 min prior to inhalation), and at 5, 10, 15, and 20 minutes into the inhalation and 15 minutes after inhalation ends. The peak effect will be obtained immediately after the end of the inhalation when the subjects will be asked to retrospectively rate the greatest intensity of effects experienced. A 26% increase in peak effect over baseline on the "fearful" item will be utilized as criteria for responding to CO₂ challenge as recommended based on prior work which suggests that approximately 50% of subjects will meet this criterion. The VAS-A "fearful" rating at 20 minutes from the start of CO₂ administration will serve as the primary outcome measure with the rating of peak effect being a key secondary outcome. The VAS-A may also be used during the anxiety task before, during, or after to measure changes in levels of subject anxiety from baseline to post-task administration.
4. **State Trait Anxiety Inventory (STAI).** The 20 item STAI will be included as a secondary clinical symptoms measure of state anxiety occurring with CO₂ administration. This was included because it has well-established psychometric properties and reflects changes in anxiety level with CO₂ administration in healthy controls and anxiolytic medication attenuated the CO₂ response with this measure. It consists of 20 items listing feelings and subjects rate their

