- None of the above

10.7 INCLUSION CRITERIA: Briefly describe the population(s) that will be involved in this study. Include anyone that data will be collected from or about (e.g. patients, healthy controls, caregivers, providers, administrators, students, parents, family members, etc.):

Inclusion/Exclusion criteria were chosen to allow us to meet study aims and are comparable to those used in [name] prior study of transcranial alternating current (tACS) vestibular stimulation of healthy controls. Inclusion Criteria. 1) Age between 21-65; 2) Use of effective method of birth control for women of childbearing capacity; 3) Willing and able to provide informed consent; 4) Have a significant difference between the mean pupil diameter in response to rare vs common tones in the Auditory Oddball Test (AOT) or the Anxiety Task; 5) The 10 subjects in the R21 cross-over study and all of the R33 subjects must have a 26% increase in VAS-A "fearful" response to 7.5% CO₂ at the first CO₂ challenge session; 6) Able to follow study procedures.

10.8 EXCLUSION CRITERIA: List any exclusion criteria (e.g. reasons why someone would not be included in the study):

Exclusion Criteria. 1) Current or past Axis I DSM-IV disorder based on the MINI; 2) Current or past history of substance abuse or dependence (excluding nicotine) based on history or positive urine toxicology; 3) Current unstable medical condition; 4) Any current neurological condition or medical condition that is known to affect pupillary function, mood/anxiety, or neurologic function generally; 5) Pregnancy based on Urine Pregnancy Test; 6) Women who are breast feeding; 7) Use of medications known to affect CNS function within 5 half-lives screening; 8) Use of magnet controlled or programmed devices such as pacemakers, programmable ventriculoperitoneal shunts, or vagal nerve stimulators.

10.9 * RESEARCH CONDUCTED ON PATIENT CARE WARDS: Do any study activities take place on patient care units at UCSF medical facilities: (REQUIRED)

Yes No

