11.0 Recruitment and Consent

11.1 * RECRUITMENT METHODS: What kinds of methods will be used to identify potential participants for recruitment (check all that apply): (REQUIRED)

- Medical records review
- Recruitment registry
- Re-contact of participants from the investigators' previous studies
- Referrals from colleagues (attach the 'Dear Colleague' letter or other recruitment materials you will provide to colleagues)
- Referrals from the community / word of mouth
- Advertisements (flyers, brochures, radio or t.v. ads, posting on clinical research sites or social media, presentation of the study at community events/media, etc.)
- Online recruiting tool such as TrialSpark
- CTSI Recruitment Services unit
- Other method (describe below)

Attach your recruitment materials (e.g., flyers, ads, recruitment letter templates, email text, etc.) in the Other Study Documents section of the Initial Review Submission Packet Form.

11.3 DETERMINATION OF ELIGIBILITY: How, when, and by whom will eligibility for recruitment be determined:

Flyers are placed around the UCSF campus and on the clinicaltrials.gov providing basic study information and eligibility criteria. Potential subjects will contact the study coordinator who will conduct a brief phone screen to determine initial eligibility criteria prior to scheduling the in-person screening visit. If the subject meets pre-screening criteria, an in-person screening visit will be scheduled at which time the subject will undergo screening procedures in [name] laboratory conducted by a study clinician. Normal healthy control subjects will be recruited and, following signing of informed consent, screened in the laboratory for whether they meet inclusion/exclusion criteria by [name] or other study clinician and a study coordinator trained by and working under the supervision of [name]. Assessments carried out during this visit will include a medical, psychiatric, and medication history, physical examination, urine drug screen, pregnancy test, and MINI. Those meeting entry criteria will then undergo the Anxiety Task or Auditory Oddball Task (AOT) administered by [name] or the study coordinator. Those with a statistically significantly greater pupil diameter response to the Anxiety Task or the cues for the rare vs common stimuli in the AOT will continue in the study and be scheduled for return visits.

Flyers will be placed around the UCSF campus and in non-investigator faculty offices.

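### As scheduled, the 26% CO2-response criterion is assessed after allocation and after tDCS, and this does not fit with 60 as the number randomised

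*Combined protocol and SAP*

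**What the plan says.** **The criterion.** Section 10.7, inclusion criterion 5, requires the ten R21 cross-over subjects and all R33 subjects to show a 26% rise in the VAS-A fearful "response to 7.5% CO₂ at the first CO₂ challenge session". Section 8.11 gives the rule as "A 26% increase in peak effect over baseline on the" fearful item and expects about half of subjects to meet it. On timing it says: "The peak effect will be obtained immediately after the end of the inhalation", by retrospective rating. The same section makes the 20-minute fearful rating the primary outcome.

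**Screening.** Section 11.3: "Assessments carried out during this visit will include a medical, psychiatric, and medication history, physical examination, urine drug screen, pregnancy test, and MINI", followed by the Anxiety Task or AOT. No CO2 challenge is listed.

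**R21 cross-over.** Section 11.13 gives four visits: screening and three study visits. In section 8.4, session 1 is titration, and at sessions 2 and 3 "subjects will receive doseoptimized tDCS and the control treatment with order randomized along with 7.5% CO₂", with tDCS in the last five minutes of the 20-minute inhalation. Section 15.3 describes all three post-screening visits as ones with tDCS.

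**R33.** Section 8.4: "60 subjects will participate in a double-blind, randomized, controlled, parallel-group trial. They will be randomized to either active or control treatment". Allocation precedes titration, because the titration procedure depends on the arm: "at the first post-screening visit they will undergo electrical dose titration as described above for the treatment they are randomized to". The CO2 session comes last, when subjects "return in 1 week and undergo optimal dose tDCS or control treatment for a single treatment session", which follows the cross-over description.

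**Counts.** The study summary and section 8.4 give 60 as the number randomised. Sections 8.4 and 10.1 plan 172 R33 enrolments, allowing for 25% pupil failure, 50% CO2 failure and an unstated rate of other screening failure.

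**Analysis.** Section 8.25 does not say how a randomised subject who fails criterion 5 is analysed.

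**The concern.** An inclusion criterion should rest on information that treatment cannot have changed. Here the qualifying rating comes at the end of an inhalation whose last five minutes carry active or control tDCS, and it uses the item on which the R33 is decided. If active tDCS works, it can lower the recalled peak and so make active subjects fail. Leaving failures out would then compare a treatment-selected active group with a differently selected control group.

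The stake differs by phase. In the R33 it is the primary comparison. In the R21 cross-over the treatment comparison in section 8.25 is on pupil diameter, so the concern is that active-first subjects are admitted under active tDCS and control-first subjects under control. The two sequences can then differ in number and in kind.

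The second problem is size. If half of subjects fail after allocation, 60 cannot be both the number randomised and the number retained.

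**Working it through.** **1. Order of events.**
- R21 cross-over: screening (no CO2), titration, then two CO2 sessions, both with randomised treatment. Section 8.9 speaks of two days of gas exposure, which matches. The first CO2 session is therefore always a treatment session, and the peak rating follows tDCS.
- R33 as described: randomisation, arm-specific titration, one CO2 session with treatment. The order is the same.

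**2. The plan's enrolment figures.** Enrolment = number needed / product of pass rates.
- R33: 60/(0.75 × 0.50) = 160, against 172. The gap corresponds to other screening loss of 1 − 160/172 = 7.0%, a rate the plan does not state, so 172 is not shown to be wrong.
- R21: 30/0.75 + 10/(0.75 × 0.50) = 40 + 26.7 = 66.7, against 68.
- Without the CO2 loss the R33 would need only 60/0.75 = 80. The plan therefore treats 60 as the number left after the CO2 filter.

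**3. Consequence if the filter follows randomisation.**
- To retain 60: 60/0.50 = 120 randomised. This is feasible from 172 (172 × 0.75 = 129 before other losses), but it is not 60.
- If 60 are randomised: 60 × 0.50 = 30 retained.
- The 95% half-width for Cohen's d near zero is 1.96 × √(2/n), with n per arm and 1:1 allocation assumed. For n = 30 it is 0.51; for n = 15 it is 0.72.
- If active tDCS lowers the pass rate to 40% or 30% (assumed), 30 per arm leave 15 control against 12 or 9 active.

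**4. Attenuation, illustrative only.** All inputs are assumed: the untreated 20-minute rise is normal with mean 26 mm and SD 22 mm, the threshold is 26 mm (so 50% pass), there is no rating noise, and tDCS halves the 20-minute rise.
- Reference, subjects who would pass without tDCS: control mean 26 + 22 × 0.798 = 43.55, SD 13.26; active mean 21.78, SD 6.63. d = −21.78/√((13.26² + 6.63²)/2) = −2.08.
- If the recalled peak follows the post-tDCS state, an active subject passes only with an untreated rise of at least 52 mm (z = 26/22 = 1.18, 12% pass). Active mean 31.4, SD 4.65. d = (31.4 − 43.55)/√((13.26² + 4.65²)/2) = −1.22, which is 41% smaller.
- If recall is perfect and 70% to 95% of the rise is reached by minute 15, simulation gives d = −1.76 to −2.04, which is 15% to 2% smaller.
- With no tDCS effect there is no bias. If 26% is read as a fraction of the baseline rating, a few scenarios gave a slight inflation of 2–3%.

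The answer turns on how the peak is recalled, which the documents do not settle. None of these figures is a bound.

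**The case against.** The strongest reply is that an R33 challenge before randomisation was intended and simply not described. Criterion 5 is labelled an inclusion criterion, CO2 failure is listed beside the other screening criteria, and the word first, together with two days of gas exposure, could point to a separate visit. On that reading 172 enrolled and 60 randomised agree and there is no selection bias. The visit list in section 11.13 covers only the R21, and the R33 returns to the IRB before it starts, so its text may be completed later. This stands as a possibility, and a reader should not infer that the R33 will certainly apply the criterion after treatment. It does not remove the need for correction: a CO2 visit would then be missing from section 8.4. Nor does it help the R21 cross-over, where the schedule is explicit and contains no CO2 session without study treatment.

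Four other inferences go too far:
- **False positive risk.** If tDCS affects no rating, both arms are filtered alike and no bias arises.
- **Dilution of d in the R21.** Its treatment comparison is on pupil diameter.
- **Only subjects below the threshold at minute 15 are affected.** The peak is recalled after tDCS, so the recall of earlier fear may also change.
- **Exclusion of failures is planned.** Section 8.25 is silent. Keeping everyone would avoid the bias, but no section says so.

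**Conclusion.** The point holds as a conflict in the written plan. In the R21 cross-over, criterion 5 is firmly placed after allocation and after tDCS. In the R33 it is placed there by the only schedule described, with an omitted earlier visit possible. If randomised failures are dropped, the retained R33 arms are no longer the randomised arms, and a true effect is generally attenuated by an undetermined amount.

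The count conflict rests on the plan's own 25% and 50% rates: about 120 randomised, or 60 randomised and about 30 retained. The half-widths further assume 1:1 allocation. It should be fixed before the R33 starts. Confidence is medium because the intended R33 order is unknown.

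**What to change.** **1. Reconcile.** State, separately for the R21 cross-over and the R33, whether the CO2 criterion is applied before or after randomisation, and whether 60 is the number randomised or the number qualifying. The study summary and sections 8.4, 8.9, 8.11, 10.1, 10.7, 11.3, 11.13 and 15.3 must agree.

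**2. If the criterion stays at the treatment session**, do not exclude on the post-tDCS peak. Write one of these into section 8.25 and use the same rule in the R21 cross-over:
- Criterion 5 is assessed only on the 5-, 10- and 15-minute ratings against baseline, completed before tDCS starts, and every qualifying randomised subject is analysed in the assigned arm.
- Every randomised subject with a 20-minute rating is analysed in the assigned arm, whatever the criterion 5 result.

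**Cost.** Neither rule needs a new visit or rating, and the R33 is to be resubmitted to the IRB anyway.
- The first replaces the peak rule and should lower the pass rate below the planned 50%, which must be restated. At assumed pass rates of 48%, 42% and 31%, 60/(0.75 × rate) gives 167, 190 and 258 enrolled before other losses.
- The second keeps CO2 non-responders and gives a smaller effect. In the illustration above, halving gives d = −13/√((22² + 11²)/2) = −0.75 in everyone. A 25% cut gives −6.5/√((22² + 16.5²)/2) = −0.33, which 30 per arm (half-width 0.51) would not separate from zero.

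If the criterion is to come before randomisation, a CO2 visit must be added: up to 129 in the R33 and 10/0.5 = 20 in the R21, 149 in all. At the R21 figures of 2–2.5 hours and $50 per visit, assumed to carry over, that is 298–373 subject-hours and $7,450.

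**3. Clarify separately** whether 26% means 26 mm on the line or 26% of the baseline rating, and whether the no-effect titration exit in section 8.9 applies in the R33 and to both arms.

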11.0 Recruitment and Consent

11.1 * RECRUITMENT METHODS: What kinds of methods will be used to identify potential participants for recruitment (check all that apply): (REQUIRED)

- Medical records review
- Recruitment registry
- Re-contact of participants from the investigators' previous studies
- Referrals from colleagues (attach the 'Dear Colleague' letter or other recruitment materials you will provide to colleagues)
- Referrals from the community / word of mouth
- Advertisements (flyers, brochures, radio or t.v. ads, posting on clinical research sites or social media, presentation of the study at community events/media, etc.)
- Online recruiting tool such as TrialSpark
- CTSI Recruitment Services unit
- Other method (describe below)

Attach your recruitment materials (e.g., flyers, ads, recruitment letter templates, email text, etc.) in the Other Study Documents section of the Initial Review Submission Packet Form.

11.3 DETERMINATION OF ELIGIBILITY: How, when, and by whom will eligibility for recruitment be determined:

Flyers are placed around the UCSF campus and on the clinicaltrials.gov providing basic study information and eligibility criteria. Potential subjects will contact the study coordinator who will conduct a brief phone screen to determine initial eligibility criteria prior to scheduling the in-person screening visit. If the subject meets pre-screening criteria, an in-person screening visit will be scheduled at which time the subject will undergo screening procedures in [name] laboratory conducted by a study clinician. Normal healthy control subjects will be recruited and, following signing of informed consent, screened in the laboratory for whether they meet inclusion/exclusion criteria by [name] or other study clinician and a study coordinator trained by and working under the supervision of [name]. Assessments carried out during this visit will include a medical, psychiatric, and medication history, physical examination, urine drug screen, pregnancy test, and MINI. Those meeting entry criteria will then undergo the Anxiety Task or Auditory Oddball Task (AOT) administered by [name] or the study coordinator. Those with a statistically significantly greater pupil diameter response to the Anxiety Task or the cues for the rare vs common stimuli in the AOT will continue in the study and be scheduled for return visits.

Flyers will be placed around the UCSF campus and in non-investigator faculty offices.

11.4 * INITIATION OF CONTACT: Who initiates contact (check all that apply): (REQUIRED)

- Investigators/study team
- UCSF recruitment unit (e.g. CTSI Consultation Services)
- Potential participant
- Other (explain below)

11.5 * HOW IS CONTACT INITIATED: (check all that apply): (REQUIRED)

- In person
- Phone
- Letter / email
- Website or app
- Other (explain below)

Attach the telephone recruitment script in the Other Study Documents section of the Initial Review Submission Packet Form. If potential participants will initiate contact, attach the telephone screening script that will be used to provide more information about the study and determine if callers are eligible to participate.

11.6 RECRUITMENT PLAN: Based on the checkboxes you chose above, please provide a narrative describing your recruitment plan. We want to know:

- Who is conducting the search for potential participants, and how?
- How are potential subjects being approached for recruitment? By whom, and when?

If there will be more than one participant group (e.g. patients, healthy controls, caregivers, family members, providers, etc.), provide details about the recruitment plans for each group. (Recommended length - 100-250 words)

Normal healthy control subjects will be recruited from the local community using posted flyers or referred by word of mouth, this study is also listed on the clinicaltrials.gov website. Individuals responding to the flyers, word of mouth or posting on clinicaltrials.gov website will contact the study coordinator and undergo a brief phone screen (phone script attached). The coordinator will schedule the subject for the inperson screening visit if they meet basic eligibility criteria.

11.7 * CONSENT METHODS: How will permission to participate (i.e., informed consent) be obtained from each potential participant. If there will be multiple groups and different plans for consenting each, check all that apply. See the orange Help bubble to the right for more detailed guidance. Participants will (check all that apply): (REQUIRED)

- Sign a consent form at the end of the consent discussion (signed consent)
- Provide online 'eConsent' using DocuSign or another E-Signature system
- Click through a link in a survey or email after reading about the study and then complete the study online (electronic consent)
- Be told about the study and be given a handout/information sheet and be asked if they agree to participate (verbal consent)

Complete the study activities and turn in materials, as in the case of a completed survey that is placed in a drop box or mailed to the study team (implied consent)

Not be able to provide consent and will have a family member consent for them, as in the case of a critically ill or unconscious patient (surrogate consent)

- Not be able to provide consent (emergency waiver of consent - allowed for minimal risk research or greater than minimal risk research with an approved community consultation plan)
- Not know about the study, as in the case of chart reviews or observations of public behavior (waiver of consent)
- Other method (describe below)

Attach your consent form, information sheet, or electronic consent text in the Informed Consent Documents section of the Initial Review Submission Packet Form.

11.8 * CONSENT PROCESS: Describe the process for obtaining informed consent, including details such as who will have the consent discussion and when participants will be asked to sign the consent form in relation to finding out about the study: (REQUIRED) We encourage researchers to review our guidance on obtaining and documenting informed consent.

- If there are multiple groups being consented differently, provide details about the consent process for each group.
- If you are relying on **verbal or implied consent**, provide details about how that will happen.
- For studies using online recruitment and consent or consent via mail, provide details here.

Written Informed Consent will be obtained from each subject prior to enrollment into the study. The process of informed consent will be carried out so as to ensure that potential subjects are properly informed as to the purpose of the study and the potential risks and benefits that are known, or that can be reasonably predicted or expected. All potential subjects will first have the study described to them verbally. This will then be followed by giving those subjects who remain interested in participating a copy of the informed consent document to review. This will then be followed by an opportunity to ask questions and express concerns. The Investigator will retain the original copy of the Informed Consent Form signed by the patient, a duplicate will be provided to the patient. Only the consent form approved by the IRB will be used. Potential subjects who do not have the capacity to give legally effective consent will not be included in this study.

* It is important that the people obtaining consent are qualified to do so. Briefly describe the training and experience these individuals have in obtaining informed consent: (REQUIRED)

The study coordinator, [name], will obtain informed consent. [name] has been involved in research for over 10 years and has over 4 years of experience obtaining informed consent. The PI may also obtain consent and he has 25 years of experience consenting subjects in clinical research studies.

11.9 * CONSENT COMPREHENSION: Indicate how the study team will assess and enhance the subjects' understanding of study procedures, risks, and benefits prior to signing the consent form (check all that apply): (REQUIRED) Tip: Review the Consent Comprehension - Learning Notes in the Help bubble at the right for specific questions that can be asked to assess comprehension, consider using the UCSF Decision-Making Capacity Assessment Tool, and review our guidance on obtaining written or verbal informed consent for more detail on how to conduct the assessment.

The study team will engage the potential participant in a dialogue, using open-ended questions about the nature of the study or the experimental treatment, the risks and benefits of participating, and the voluntary nature of participation

Potential participants will be asked or shown a series of questions to assess their understanding of the

study purpose, procedures, risks and benefits, as well as the voluntary nature of participation (especially appropriate when the consent process happens online or through a mobile health app)
Other method (describe below):

Provide details of the other approaches that will be used, if using another method to assess comprehension:

11.13 TIME: What is the estimated time commitment for participants (per visit and in total):

Estimates for the R21 portion of the effort are included here:

For enrolled subjects 1-30, there are up to three total visits each scheduled 1 week apart. Screening procedures will take place at the first visit and will be combined with study procedures if the subject passes screening. The first visit will take 2 hours and the remaining 2 study visits will take 1.5 hours each for a total study commitment time of 5 hours.

For the last 10 enrolled subjects, there are four total visits scheduled 1 week apart: Screening + 3 study visits. Screening will take between 1-1.5 hrs and the remaining 3 study visits will take 2-2.5 hrs each for a total study commitment time of 7-9 hours.

IMPORTANT TIP: Ensure this information is consistent with the information provided in the consent form.

